Aim 2: ACT Mediators. Acceptance of internal cues to smoke: Measured using the Avoidance and Inflexibility Scale (AIS; $\alpha = .93$; [16, 20], which assesses one's willingness to experience sensations (9 items), emotions (9 items), and thoughts (9 items) that cue smoking. A sample item for the sensations scale is: "To what degree did you allow yourself to have urges to smoke?" Commitment to quitting. Commitment to quitting despite internal (e.g., cravings, anxiety) and external (e.g., smoking in the social environment) cues to smoke will be measured using the Commitment to Quitting Scale (CQS; $\alpha = .93$; [59]). Sample item: "No matter how many people around me smoke, I won't let myself smoke once I quit." Regarding assessment timing, three months post randomization is when we expect acceptance and commitment to increase the most, as consistent with past ACT smoking cessation studies [16, 17, 20, 82], and would allow testing of our hypothesized model of increases in acceptance and commitment at three months mediating the impact of the intervention on smoking cessation by twelve months.

Aim 3: Costs of delivery, for cost-effectiveness analyses. Costs associated with each app's delivery include the cost to: (1) host the servers and databases, (2) conduct software updates to accommodate ongoing changes in operating systems, (3) have programming staff to answer technical questions, and (4) cost of facilities and equipment needed to maintain each (e.g., office space for personnel, computers). NCI, the host of QuitGuide, has agreed to provide these costs for QuitGuide [32]. Research-related costs will not be included.

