Analyses. Aim 1. Our primary outcome hypothesis is that iCanQuit will have significantly higher 30-day point prevalence abstinence at 12 months post-randomization than QuitGuide. **Analyses:** For each comparison of the arms on the primary and all secondary endpoints, we will use a logistic regression model with complete case smoking cessation outcome [9-14]. The model will adjust for all stratification factors as well as baseline factors that might be imbalanced after randomization. In addition, we will conduct these analyses: (1) multiple imputation of missing outcomes [90-92], (2) missing equals smoking outcomes [9-14], (3) using a secondary cessation outcome of no use of cigarettes **and** other nicotine or tobacco products except FDA-approved nicotine replacement therapies. Finally, we will compare the two arms on utilization of their assigned app.

Aim 2. We hypothesize that the iCanQuit arm's (but not the QuitGuide arm's) smoking cessation outcomes will be strongly mediated by these psychological measures that are central to the theoretical model underlying ACT: commitment to quitting and acceptance of internal (a) sensations, (b) emotions, and (c) thoughts that cue smoking. This hypothesis is consistent the ACT model and prior ACT for smoking cessation intervention studies [16, 17, 20, 82]. **Analyses:** For each mediator, the model is expressed as three regression equations that relate the main independent variable X

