(ACT intervention), the mediator M (change from baseline to 3-months post randomization in the acceptance variable, and/or commitment to quitting smoking despite internal cues), and the binary endpoint Y at 12-months post-randomization (e.g., 30-day abstinence). The first regression describes the total intervention effect (X) on the outcome (Y): $\text{logit}(Y) = \gamma_1 + \tau X$, where the parameter τ measures the total intervention effect. The second regression describes the impact of the intervention (X) on the mediator (M): $M = \gamma_2 + \alpha X$. The third regression describes the simultaneous impacts of the intervention (X) and mediator (M) on the outcome (Y): $\text{logit}(Y) = \gamma_3 + \tau'X + \beta M$. Since the endpoint is binary, the mediation effect is the product term $\alpha\beta$, whose empirical distribution will be estimated via 5000 bootstrapped samples. Bootstrapping is a resampling method which provides a powerful test of mediation that does not rely on normality assumptions [93-95]. Randomization should remove potential confounding effects [92, 93], and if needed, we will adjust each model by covariates that differ at baseline or predict outcome. Following VanderWeele and Preacher methods [94, 95], we will also explore any interactions between mediators and treatment arm. And we will explore whether utilization of assigned app and usage of cessation pharmacotherapy mediates cessation outcomes.

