
Exploratory Aim. This aim will explore whether iCanQuit, as compared to QuitGuide, has higher quit rates for those with these baseline factors: (a) those scoring low on acceptance of sensations, emotions, and thoughts that cue smoking, (b) heavy smokers (≥ 20 cigarettes/day), (c) smokers screening positive for mental health symptoms, and (d) being a racial/ethnic minority. **Analyses:** This aim will explore key moderators of ACT treatment outcomes and aid in the critical effort to improve quit rates for these high-risk groups [101-105]. The ACT model suggests that, in addition to being a key mechanism (i.e., mediator) of treatment, baseline acceptance is a moderator of treatment outcome [22]. Specifically, we hypothesize that people who avoid their

triggers to smoke (i.e., low acceptance) will benefit most from ACT because ACT teaches skills to overcome avoidance. We also hypothesize that this focus on acceptance may be especially helpful for heavy smokers and those with mental health symptoms because physical, emotional, and cognitive cues to smoke are stronger for these individuals [106-109]. Finally, testing moderation by race/ethnicity will allow us to generate hypotheses about whether minorities overall respond differently to ACT than non-Hispanic Caucasians. We will explore moderation with separate logistic regression models for each moderator variable, where 30-day abstinence at 12-months post randomization is the outcome (Y). The model will include the moderator (Z), group assignment (X), and an interaction between moderator and group assignment (X*Z). Statistically significant interactions will be assessed with plots showing how the slope of Y on X is dependent on the value of Z. The slopes will be derived from logistic regressions that correspond to the prediction of Y from X at a single value of moderator Z.

Power. We determined sample size with 5,000 iterative simulations aimed at 80% power for Primary Aim 1. We used the following parameters: (1) participants randomized to one of the two arms; (2) two-sided test with $\alpha = .05$; (3) intent-to-treat analysis where, as standard in smoking cessation trials, all those with missing data are coded as smokers [11, 60]. The calculations do not account for potentially higher effect sizes from the adjustment of stratification factors.

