We will conduct a fully-powered two-arm randomized controlled trial that compares iCanQuit to QuitGuide, which follows the USCPG [67]. To balance baseline variables between the two conditions, we will stratify randomization by daily smoking frequency (≤ 20 vs. ≥ 21), education (\leq high school vs. \geq some college), race/ethnicity (minority race/ethnicity vs. non-Hispanic White) and depression screen (CES-D score ≤ 15 vs. ≥ 16). Moderators will be measured at baseline. Mediators will be measured at baseline and three months post randomization. Cessation and cost-effectiveness outcomes will be measured at 3, 6, and 12 months post randomization. Enrollment and baseline data collection will occur via a SSL secured website hosted by Fred Hutch. The ACT intervention will occur on an app platform which will send, via 256-bit SSL encryption, study-ID coded usage data from smartphones to secured Fred Hutch servers. Outcome surveys occur via an online-telephone-mailed sequence conducted by Fred Hutch.

Sources of material

As shown in Table 3 of the Research Plan, these are sources of survey data for the study: (1) screening survey, (2) baseline survey, (3) 3-month follow-up survey, (4) 6-month follow-up survey, and (5) 12-month follow-up survey. We will also collect automated utilization data from both apps. A description of these sources of data follows.

Survey Data

As further outlined in Table 4 and Research Plan, the Baseline Survey, hosted on our secured recruitment website, will collect data on (1) demographics, (2) current smoking status and smoking history, (3) readiness to quit, (4) nicotine dependence, (5) acceptance of internal cues to smoke, (6) commitment to quitting, (7) quality of life, (8) mental health, and (9) contact information needed for the study's follow-up data collection activities – as well as information about whether or not it is acceptable to receive email or voice messages and mail from the study. The Three-Month survey will primarily collect data on cessation processes (e.g., acceptance of cues to smoke), progress (e.g., quit attempts) and outcomes (e.g., 30-day abstinence), and the participant's experiences with their assigned smoking cessation intervention. The Six and Twelve Month surveys will primarily collect data on cessation progress and outcomes.

App utilization data and security

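### Aim 2 relies on randomisation to remove confounding of the mediator-to-outcome path, which it cannot do, and does not fix whether the baseline mediator enters the change-score models.

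*Combined protocol and SAP*

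**What the plan says.** Under Analyses, Aim 2, the mediator M is the "change from baseline to 3-months post randomization in the acceptance variable" (and/or commitment). Three regressions follow: Y on arm X, M on X (slope α), and Y on X and M (slope β for M). None contains a covariate. The mediation effect is αβ, tested by bootstrap.

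On confounding, the section says only: "Randomization should remove potential confounding effects [92, 93], and if needed, we will adjust each model by covariates that differ at baseline or predict outcome". Aim 1 is firmer: "The model will adjust for all stratification factors as well as baseline factors that might be imbalanced after randomization".

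Four other statements bear on this:
- Aim 2: ACT Mediators gives the hypothesis as "increases in acceptance and commitment at three months mediating the impact of the intervention on smoking cessation by twelve months".
- The Exploratory Aim analysis says "baseline acceptance is a moderator of treatment outcome".
- Survey Data says the three-month survey collects "cessation processes (e.g., acceptance of cues to smoke), progress (e.g., quit attempts) and outcomes (e.g., 30-day abstinence", so early quitting is recorded together with the mediator.
- The Aim 2 hypothesis is that the "iCanQuit arm's (but not the QuitGuide arm's) smoking cessation outcomes will be strongly mediated". On arm differences in the mediator slope, the plan says "we will also explore any interactions between mediators and treatment arm".

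**The concern.** Arm is randomised, but the change in acceptance or commitment is not. Anything that makes a person both raise their acceptance and quit will bias β, and αβ carries that bias. Balance between arms is no safeguard, since a covariate perfectly balanced across arms can still cause both M and Y. Baseline imbalance is therefore the wrong trigger for adjustment here. Predicting the outcome is a better one, but it is conditional and no covariates are named.

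The baseline mediator is the clearest case. A change score is negatively correlated with its own baseline. If baseline acceptance also bears on outcome, as the Exploratory Aim supposes, it is related to both M and Y, yet the third equation omits it. Early quitting by 3 months is another possible common cause, and the plan does not say how it is handled.

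Aim 2 is meant to identify which ACT processes need further work. A halved or spurious indirect effect would misdirect that. The estimate could also depend on how the adjustment clause is read once the data are in.

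**Working it through.** **The plan's own figures.** For 11% vs 7%, two-sided 5%, 80% power, pooled variance: n per arm = [1.960·√(2·0.09·0.91) + 0.842·√(0.11·0.89 + 0.07·0.93)]² / 0.04² = 803, so 1606 in total against the stated 1622. Power at 811 per arm is 80.4%. The Aim 2 power claim (over 99%) cannot be checked uniquely because α and β are not given separately. That is a different point and is not counted here.

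**Targets.** Total log OR = ln(0.11/0.89) − ln(0.07/0.93) = 0.496. The Power section assumes that commitment explains 25% (0.25 × 0.496 = 0.124) and acceptance 60% (0.60 × 0.496 = 0.298).

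**Why the baseline value matters.** Let baseline M0 and 3-month M3 have equal variances and correlation r, and let D = M3 − M0.
- corr(D, M0) = −√((1−r)/2) = −0.59, −0.50, −0.39 for r = 0.3, 0.5, 0.7.
- If Y depends on M3, the slope on D alone is about cov(M3, D)/var(D) = (1−r)/(2(1−r)) = 1/2 of the true slope, whatever r is.

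**Simulation inputs.** From the documents: 811 per arm, 7% and 11%. Assumed: arm effect on the mediator 0.3 SD, the three values of r, equal variances. Model: M3 = r·M0 + √(1−r²)·e + 0.3X. The test is joint significance of α and β at two-sided 5%, in place of the bootstrap, with 1500 replicates for cases A, B and C. The clause is read, by assumption, as adding M0 to both equations if p < 0.05 in logit(Y) on X and M0.

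**A. Change alone drives quitting, no common cause.** No bias: commitment product 0.124–0.125 as written.

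**B. The 3-month level drives quitting; commitment, true product 0.124** (r = 0.3, 0.5, 0.7).

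| Model | Product | Power |
|---|---|---|
| As written | 0.061 | 79%, 66%, 45% |
| Clause (M0 admitted in 28%, 65%, 91% of trials) | 0.083, 0.107, 0.121 | 91%, 94%, 90% |
| M0 always in | 0.124–0.125 | 99%, 98%, 92% |

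For acceptance (true 0.298) the product is 0.136–0.139 as written, 0.280–0.296 with the clause and 0.296 with M0 always in. Power is at least 97% throughout.

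**C. Baseline acceptance moderates the effect; no mediator effect.** Assume QuitGuide quits at 7% throughout and iCanQuit at 13% below and 9% above median baseline acceptance. The written equations give a product of 0.022 and declare mediation in 18%, 15%, 11% of trials. A 12%/10% split gives 7–9%, and 14%/8% gives 18–35%. With the 13%/9% split, the clause brings this to 5–6% and M0 always in to 5%. If the gap lies in QuitGuide instead (5% low, 9% high; iCanQuit 11% in both), the product is −0.024, so the direction is not known in advance. If the arm does not move the mediator, the rate is under 1%.

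**D. Omitted common cause U, no mediator effect (illustration).**
- Mimicking the whole commitment effect needs corr(U, D) × ln(OR) ≈ 0.124/0.3 = 0.41: correlation 0.3 with OR 4.0 per SD, 0.4 with 2.8, or 0.5 with 2.3 (simulated product 0.106–0.119).
- About half of it (0.060) needs 0.3 with OR 2.0, or 0.5 with 1.5.
- False declarations at 811 per arm (400 replicates): 12% for correlation 0.2 and OR 1.3, 29% for 0.3 and 1.5, 86% for 0.4 and 2.0. At 1250 per arm: 13%, 41%, 95%. With U in both equations: about 5–7%.
- Early quitting: assume 3-month rates of 8% and 13% (the pilot's two-month rates), quitters 0.25–0.5 SD higher on M, and 35–50% of them abstinent at 12 months. The product is 0.025–0.083. It is about 0 with 3-month abstinence in the third equation, and at most 0.006 if the arm has no other effect on M.

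**The one-arm claim.** α is a difference between arms, so αβ is a single between-arm quantity. It cannot show mediation in one arm and its absence in the other.

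**The case against.** The adjustment clause has two routes, and the second, covariates that predict outcome, applies to every model and would admit a measured common cause. Read that way, it removes nearly all the false mediation in case C and restores commitment power to 90–94% in case B. At the expected retained size (1250 × 0.84 = 1050 per arm), case B power is 54–88% as written but 96–99% with the clause and 97–100% with the baseline always in. The hypothesis is worded in terms of change, and under that model there is no bias. Case C concerns acceptance only, the subgroup rates are invented, and mimicking the whole commitment effect takes a strong omitted cause. Three-month abstinence may lie on the causal path, so omitting it is defensible. Mediator-by-arm interactions are at least to be explored.

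Much of this stands, and it limits the size. Halving needs both a level-driven process and an unused clause. Even with the clause used, the product at 1050 per arm is 0.085 at r = 0.3, against 0.115 and 0.122 at r = 0.5 and 0.7. None of it rescues the statement about randomisation, and a conditional clause without named covariates leaves the choice until after the data are seen. Exploring interactions does not turn αβ into an arm-specific result.

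**Conclusion.** The concern holds. The statement about randomisation is wrong for β, nothing elsewhere in the document corrects it, and the clause neither commits to adjustment nor targets common causes of mediator and outcome. Confidence is high on the principle and moderate on the sizes, which rest on the assumed 0.3 SD arm effect, equal variances and r of 0.3–0.7.

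Under those assumptions the commitment estimate ranges from about half to nearly all of its true value depending on how the clause is read, if the 3-month level drives quitting. It is unbiased if only change does and there is no common cause. The acceptance tests keep their power, but without the clause the acceptance estimate is also about halved. Aim 1 and the sample size are untouched. This should be fixed before the Aim 2 analysis.

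**What to change.** 1. Always include the baseline value of each mediator in the second and third equations.
2. Replace the randomisation sentence with an explicit assumption of no unmeasured mediator-outcome confounding. Always adjust both equations for the stratification factors, as Aim 1 does, plus a fixed list of baseline predictors of quitting already collected (for example nicotine dependence, Table 4).
3. Add a sensitivity analysis stating how strong an omitted common cause would have to be to explain the result. Add a second, labelled sensitivity analysis with 3-month abstinence in the third equation. That variable is post-randomisation, so this does not replace the main estimate.
4. Word the conclusion as mediation of the between-arm difference, and drop the claim of mediation in one arm only. Label interaction-based indirect effects as between-arm contrasts. Call them rare-outcome approximations on the log-odds scale, or report standardised risk differences.

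The cost is SAP wording and two sensitivity analyses, with no new data. If change alone drives quitting, always including the baseline mediator removes no bias and costs up to 3.0 points of power for commitment (95.7% to 92.7% at r = 0.7, 811 per arm).

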Aim 3. Determine whether iCanQuit is significantly more cost-effective than QuitGuide, as measured by cost per additional quitter, incremental cost-effectiveness ratio (ICER), and incremental cost per quality-adjusted life year (QALY). Importance of

this aim: will provide payers (e.g., insurance companies) and policymakers results needed to decide whether to adopt iCanQuit.

[figure not shown]
Exploratory Aim: Explore whether iCanQuit, as compared to QuitGuide, has higher quit rates for those with these baseline factors: (a) low acceptance of sensations, emotions, and thoughts that cue smoking, (b) heavy smoking (≥ 20 cigarettes/day), (c) current mental health symptoms, and (d) being racial/ethnic minority. Importance of this aim: will potentially identify key subgroups that benefit most from iCanQuit, and thereby aid in reducing tobacco-related health disparities.

Innovations. (1) ACT's innovative features augment the US Clinical Practice Guidelines; (2) ACT follows an innovative theory: Relational Frame Theory; (3) ACT on the smartphone is novel; (4) First randomized trial of a smartphone app for adult smoking cessation; (5) The first time that the following have been tested for **any** behavior outcome: (a) ACT delivered via smartphone, (b) mediation of the effects of a smartphone app, (c) cost-effectiveness of a smartphone app, and (d) exploration of subgroups who benefit most from a smartphone app. While there are thousands of apps and hundreds for smoking [2], testing an app's efficacy is scientifically innovative. That's a critical gap this application fills.

Approach

Randomized trial experimental design. We will conduct a fully-powered two-arm randomized controlled trial that compares iCanQuit to QuitGuide, which follows the USCPG. To balance baseline variables between the two conditions, we will stratify randomization by daily smoking frequency (≤ 20 vs. ≥ 21), education (\leq high school vs. \geq some college), race/ethnicity (minority race/ethnicity vs. non-Hispanic White) and depression screen (CES-D score ≤ 15 vs. ≥ 16). Moderators will be measured at baseline. Mediators will be measured at baseline and three months post randomization. Consistent with cessation trial designs [60], cessation and cost-effectiveness outcomes will be measured at 3, 6, and 12 months post randomization.

Figure 1. Experimental Design

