Aim 3. We hypothesize that iCanQuit will be more cost-effective than QuitGuide, as measured by cost per quitter, incremental cost-effectiveness ratio (ICER), and incremental cost per quality-adjusted life year (QALY). We will use current good practices of estimating cost-effectiveness, which were articulated by [96], as applied to smoking cessation interventions [77, 97]. First, to examine whether iCanQuit costs less than QuitGuide to help a person quit, we will estimate the incremental cost-per-quitter: difference in total cost of delivering the two interventions [98] divided by the difference in the number of 30-day abstinent participants at 12-months ($\text{Total Cost}_{\text{iCanQuit}} - \text{Total Cost}_{\text{QuitGuide}} / \# \text{Abstinent}_{\text{iCanQuit}} - \# \text{Abstinent}_{\text{QuitGuide}}$). Total delivery cost assessments are described in Section 3.3.11. Second, to estimate whether iCanQuit costs less than QuitGuide per life year added [77], we will calculate standard Incremental Cost-Effectiveness Ratios (ICER): $\text{Total Cost}_{\text{iCanQuit}} - \text{Total Cost}_{\text{QuitGuide}} / \# \text{Life Years Added}_{\text{iCanQuit}} - \# \text{Life Years Added}_{\text{QuitGuide}}$. Life years added attributable to each intervention's 12-month primary endpoint effect size will be derived from the life years estimates, reported in Stapleton & West [77], that conservatively account for gender, age, discounting, relapse, and unaided cessation. Third, to examine whether iCanQuit costs less than QuitGuide to add greater quality to each life year added [93], a separate ICER quality of life analysis called incremental cost-per-QALY will be conducted ($\text{Total Cost}_{\text{iCanQuit}} - \text{Total Cost}_{\text{QuitGuide}} / (\text{QALY}_{\text{iCanQuit}} - \text{QALY}_{\text{QuitGuide}})$). This analysis will be calculated by adding a Generalized Linear Model-based weighted quality of life parameter derived from the standard EQ-5D quality of life measure [99] taken at the 12-month endpoint. Finally, we will conduct multi-way sensitivity analyses of these results using 1000 Markov Chain Monte Carlo simulations that will derive a cost-effectiveness plane (and 95% CI ellipse) across a range of total costs and effect sizes. In all estimates, we will adjust future costs to a standard reference year and discount future costs and benefits incurred after one year at 3% per annum as is recommended by the USPSTF on cost-effectiveness in health and medicine [100].

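### Does Aim 3 discount life-years twice, and divide app-level costs by trial-arm counts?

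*Combined protocol and SAP*

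**What the plan says.** **Discounting (Analyses, Aim 3).** The life-year ratio uses published estimates applied to the 12-month effect. The plan describes them as estimates "that conservatively account for gender, age, discounting, relapse, and unaided cessation". It does not give their discount rate. The paragraph ends: "In all estimates, we will adjust future costs to a standard reference year and discount future costs and benefits incurred after one year", with the rate set at 3% a year. The QALY ratio is introduced as asking what it costs "to add greater quality to each life year added", with a quality weight from the EQ-5D at 12 months. Under Randomized trial experimental design, "cessation and cost-effectiveness outcomes will be measured at 3, 6, and 12 months post randomization".

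**Costs (Primary assessments, Aim 3: Costs of delivery; Analyses, Aim 3).** The delivery costs are hosting, the cost to "conduct software updates to accommodate ongoing changes in operating systems", programming staff, and facilities and equipment. Research costs are excluded. "NCI, the host of QuitGuide, has agreed to provide these costs for QuitGuide". The cost-per-quitter ratio is the difference in total delivery cost "divided by the difference in the number of 30-day abstinent participants at 12-months". The same cost difference is then divided by differences in life-years and in QALYs. Multi-way sensitivity analyses vary total costs and effect sizes.

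**The concern.** The discounting sentence covers all estimates and exempts none. Trial outcomes stop at 12 months, so the imported life-years, and QALYs if built on them, are the only benefits in Aim 3 that fall after one year. An analyst who applied the sentence mechanically would discount figures that already include a discount. The denominator would shrink and the ratio would grow. If iCanQuit both costs more and gains more, it would then look less cost-effective than it is.

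On costs, the listed items are the running costs of a whole app, and QuitGuide is a free public app whose costs come from its host. The denominator counts trial participants. If one total covered the public user base and the other only a trial arm, or if the periods differed, part of the cost difference would reflect scale and not the apps. Aim 3 is meant to inform payers and policymakers who must decide on adoption, so a distorted ratio would matter to them.

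**Working it through.** Aim 3 states no cost, life-year or ratio, so there is no figure to reproduce. The check sets the passages side by side and asks what each reading would do.

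**1. A second discount.** A gain in year k, discounted again at 3% after the first year, is multiplied by 1.03^-(k-1), so the ratio grows by 1.03^(k-1):

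- k = 10: 1.03^9 = 1.30
- k = 20: 1.03^19 = 1.75
- k = 30: 1.03^29 = 2.36
- k = 40: 1.03^39 = 3.17

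The values of k are assumptions; the documents do not say when the life-years accrue. The calculation also needs a stream of gains dated by year. The reference list titles the source as a direct method with ready-made ICER tables. If it reports discounted totals, which cannot be checked here, there is no year-by-year gain to discount again.

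**2. One discount, at the source's rate.** This is the ordinary reading, and it leaves one unknown: whether that rate is 3%. For gains spread evenly over years 20 to 29 (assumed), life-years discounted once at rate r, relative to 3%, are:

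- r = 1.5%: 1.41
- r = 3%: 1.00
- r = 3.5%: 0.89
- r = 5%: 0.64

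An analyst with the source in hand sees the rate and can report it or re-base to 3%.

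**3. Totals against per-participant figures.** Let m be mean delivery cost per participant and p the abstinence proportion, with 1250 per arm:

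(1250·m_A − 1250·m_B) / (1250·p_A − 1250·p_B) = (m_A − m_B) / (p_A − p_B).

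If costs are those of serving the trial arms, the plan's ratio is already the per-participant ratio. Rewriting it changes nothing.

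**4. Can the cost mismatch be sized?** The rates in the Power section give 1250 × (0.11 − 0.07) = 50 extra quitters. Take two apps with equal true cost and let QuitGuide have U users.

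- *Constant cost c per user, QuitGuide costed for all U users:* c × (1250 − U) / 50. U = 2500 gives −25c. U = 8000 gives −135c. The 8000 is 3.2 million downloads / 400 apps, an average over all cessation apps and not a QuitGuide figure.
- *Fixed cost C per app, only QuitGuide apportioned to its trial arm:* C × (1 − 1250/U) / 50. With C = $200,000 (assumed), U = 10,000 gives $175,000 / 50 = $3,500, and U = 100,000 gives $197,500 / 50 = $3,950.
- *Fixed cost C per app, both treated alike:* 0 / 50 = 0.

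The first two have opposite signs, so the documents establish neither a size nor a direction. Servers, updates and staff are also closer to fixed costs than to a constant cost per user.

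**5. Period.** Against 12 months, a fixed cost over recruitment plus follow-up is (17 + 12) / 12 = 2.42 times as large; over the 13 intervention quarters in Table 5 it is 39 / 12 = 3.25 times. The 17 months do not fit the 2500 target: 78 × 17 = 1326, while 2500 / 78 = 32 months. With staggered entry, the full delivery window is what serving the arms takes, so 12 months is not an obvious standard. A common period scales the difference in fixed costs without changing its sign.

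**The case for a change.** The strongest case for a change is that the accounting choice alone could decide the sign. The plan asks whether iCanQuit costs less than QuitGuide, and step 4 shows that unequal treatment of two equally costly apps could make iCanQuit look cheaper or dearer. The sensitivity analysis does not settle this: its cost range is not given, it defines no base case, and discounting is not among the items varied. Citing good-practice guidance does not state which users and period apply here. The cost description is cross-referenced to a Section 3.3.11 that matches no numbered heading in the text. The discounting sentence does say all estimates, and no other benefits in Aim 3 fall after one year.

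What stands is that two details are unwritten: how the 3% rule treats life-years already discounted (and at what rate), and the period, users and allocation behind each total. What does not stand is that the plan directs a wrong calculation. Double discounting requires the analyst to ignore the plan's own description of the life-years. The 3% rule still has work to do without it, because it also covers costs and delivery runs beyond one year. A mismatched numerator requires treating the two apps differently, and nothing in the plan calls for that. The numerator is the cost of delivering the two interventions and carries the same arm labels as the denominator. The cited guidance concerns cost-effectiveness analysis alongside clinical trials. The section App utilization data and security has both assigned apps activated by a code from the enrollment email and sending usage data to the study's servers. The unmatched section number is most likely a clerical leftover, since the cost paragraph under Primary assessments supplies the description.

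**Conclusion.** No change to the plan is needed. Both points are missing detail that a health economist would fill in one sensible way: discount benefits once, state the source's rate or re-base to 3%, say whether QALYs rest on the same life-years, and cost both apps for serving their trial arms over the same period. These choices can be reported with the Aim 3 results.

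The only size available for the discounting point is conditional: 1.30-fold at year 10 and 1.75-fold at year 20 if the rule were applied twice, with assumed timing. No size or direction can be given for the costing point, because the documents contain no delivery cost and no QuitGuide user count. Even on the worst reading, discounting leaves cost per quitter unaffected and does not alter which app gains more. Aim 1, the primary endpoint and the sample size are untouched. The conclusion rests on reading the life-year description as meaning what it says, and the cost totals as arm-level costs treated alike.
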